### 5.7.3 7-day Average of the Peak Pruritus NRS - Primary

Calculated as the average of non-missing values of the daily NRS if there are 50% or more days with non-missing values within each visit window, otherwise it will be set to missing. In addition, any data after the on-study initiation of prohibited or rescue medication will be set to missing values.

#### **5.7.4 The All Available 7-day Average of the Peak Pruritus NRS - Sensitivity**

Calculated as the average of all non-missing values of the daily NRS within each visit window. The NRS will be set to missing after the on-study initiation of prohibited or rescue medication.

#### **5.7.5 5D-Pruritus Scale**

The 5-D Pruritus Scale is a 1-page, 5-question, validated questionnaire used in clinical trials to assess 5 dimensions of background itch: degree, duration, direction, disability, and distribution.

Each question corresponds to 1 of the 5 dimensions of itch; subjects will rate their symptoms over the preceding 2-week period as “present” or on a 1 to 5 scale, with 5 being the most affected.

The scores of each of the five domains are achieved separately and then summed together to obtain a total 5-D score. 5-D scores can potentially range between 5 (no pruritus) and 25 (most severe pruritus). The score will be set to missing in case where at least one of the five domain results is missing.

- Single-item domain scores (duration, degree, and direction) are equal to the value in the response choice (range 1–5).
- The disability domain includes four items that assess the impact of itching on daily activities: sleep, leisure/social activities, housework/errands, and work/school. The score for the disability domain is achieved by taking the highest score on all available items.
- For the distribution domain, the number of affected body parts is tallied among all available items (potential sum 0–16) and the sum is sorted into five scoring bins: sum of 0–2 = score of 1, sum of 3–5 = score of 2, sum of 6–10 = score of 3, sum of 11–13 = score of 4, and sum of 14–16 = score of 5.

#### **5.7.6 Eczema Area and Severity Index (EASI)**

The EASI is a composite score ranging from 0 to 72 that takes into account the degree of erythema, induration/infiltration (papules), excoriation, and lichenification (each scored from 0 to 3 separately) for each of 4 body regions, with adjustment for the percentage of BSA involved for each body region and for the proportion of the body region to the whole body.

#### **5.7.7 Validated Investigator Global Assessment (vIGA)**

The vIGA is a global assessment of the current state of the disease. It is a 5-point morphological assessment of overall disease severity. The vIGA (excluding hands and feet) will be assessed before the morning investigational product administration.

#### **5.7.8 Body Surface Area Involvement of Atopic Dermatitis**

The overall BSA affected by AD (total BSA) will be evaluated (from 0% to 100%).

#### **5.7.9 The Patient-Oriented Eczema Measure (POEM)**

The POEM is a self-assessment of disease severity by the participant; the participant’s response to 7 questions is scored from 0 to 4; the POEM is the sum of the 7 scores, which ranges from 0 to 28. The higher the POEM, the severer the disease.

If missing items occur the following rules will be followed:

- If 1 question is left unanswered this is scored 0 and the scores are summed and expressed as usual out of a maximum of 28.
- If > 1 questions are left unanswered the questionnaire is not scored.
- If > 1 response options are selected for a single question, the response option with the highest score should be recorded.

### 5.7.10 Dermatology Life Quality Index (DLQI)

The DLQI is a 10-item questionnaire used to measure the impact of skin disease on the quality of life of an affected patient.

Generally, questions are scored on a four-point Likert scale:

- Very much = 3
- A lot = 2
- A little = 1
- Not at all = 0
- Not relevant = 0
- Question unanswered = 0

For question 7, the first part asks: “Over the last week, has your skin prevented you from working or studying?”

If working or studying are not relevant to the subject, the response is “Not relevant” (scored 0).

If the skin disease has prevented the subject from working or studying, the answer is “Yes”. As “prevention” is the biggest possible impact it is scored the maximum, 3.

If the skin disease has not prevented the subject from working or studying, the answer is “No”. It is therefore assumed that as the skin disease has not prevented the subject from working or studying, the subject is able to continue to work or study, but that the skin disease may be a problem while doing so.

The subject is therefore asked the following question about the magnitude of the impact thus: “If ‘No’ (in other words ‘If the skin disease has not prevented you from working or studying’), over the last week how much has your skin been a problem at work or studying?”

There are three possible responses to the question “How much has your skin been a problem at work or studying”: “A lot” (scored 2), “A little” (scored 1) or “Not at all” (scored 0).

The DLQI can be classified into 6 subscales: symptoms and fillings (questions 1 and 2), daily activities (questions 3 and 4), leisure (questions 5 and 6), work and school (question 7), personal relationships (question 8 and 9), and treatment (question 10).

The DLQI is calculated by adding the score of each question, ranging from 0 to 30. The higher the score, the more quality of life is impaired. A score higher than 10 indicates that the patient's life is being severely affected by their skin disease.

For this study, if one question is unanswered, this is allocated a score of 0 and the DLQI score summed in the usual way. If two or more questions are unanswered, the questionnaire is not scored.

## **5.8 Handling of Missing Values**

Missing values will not be imputed unless specified otherwise.

For the efficacy analysis of 7-day average of the daily peak pruritus NRS as specified in section 5.7 the missing values will be imputed implicitly with MMRM modeling under assumption of missing at random (MAR).

Refer to [Appendix 1](#) for the handling of partial dates in AE or concomitant medication data.

## **6 STATISTICAL CONSIDERATIONS**

### **6.1 General Statistical Considerations**

The significance level for this trial is set to be 2-sided 0.05 unless otherwise specified. For PK data, geometric mean and percent of coefficient of variance (%CV) will be presented.

All decimal places will be kept to 3 places or less.

### **6.2 Interim Analysis**

No interim analysis is planned.

## 7 STUDY PARTICIPANTS

### 7.1 Disposition of Participants

All participants who provide informed consent will be accounted for this study. The number of participants screened, and screen failure will be summarized.

Screen failures:

- Screen failures and the reason for screen failure will be listed.
- Those who were rescreened and did not fail the re-screening(s) are not considered as screen failures.
- A participant can still be a screen failure post randomization but before Day 1 due to the lack of drug availability at the time of randomization when a participant's eligibility is re-evaluated post randomization and prior to the first dose.

The number and percent of participants who are

- Randomized.
- Withdrew consent post randomization.
- Screen failure post-randomization but before Day 1.
- Screen failure at Day 1.
- Eligible to continue and receive the first dose of IP on Day 1.

will be summarized descriptively.

Study completion status and the reason for study treatment discontinuation will also be presented.

Unless otherwise specified, the denominator of the percentages will be based on the number of participants in the mITT analysis set.

The percentage of screen failures will be calculated based on the total number of participants screened as the denominator. The percentage of screen failure by reasons will be based on the number of total screen failures as the denominator.

Number of days in the study will be calculated as follows:

$$\text{Number of days in study} = \text{Date of completion/discontinuation} - 1^{\text{st}} \text{ dose date} + 1$$

A listing of participant's disposition will be provided. For those who were rescreened, data on the initial screening, including the rescreening participant identifier, will be presented under the initial screening participant identifier. A listing of participant's randomization data and a listing of participants included in each of the study analysis sets will also be provided.

In addition, participants who are excluded from the per protocol set and the reason of being excluded will be provided in a separate listing.

### 7.2 Protocol Deviations

The number of events and the number and percentage of participants with at least 1 major protocol deviation, as identified during the conduct of the clinical trial, will be summarized by deviation category and treatment group using the safety set. A listing of all major protocol deviations will also be provided, with a flag indicating if any protocol deviations led to a participant being excluded from the PP Set.

## **8 DEMOGRAPHIC AND OTHER BASELINE CHARACTERISTICS**

Demographics and baseline characteristics will be summarized with descriptive statistics using the safety set.

A listing of all demographics and baseline characteristics will be provided.

## **9 MEDICAL AND SURGICAL HISTORY**

Medical and surgical history will be coded according to the Medical Dictionary for Regulatory Activities (version 26.1 or later).

Medical and surgical history will be summarized by system organ class (SOC), preferred term (PT), and treatment using the safety set. A participant who experienced the same medical and surgical history event multiple times will be counted only once for the corresponding PT.

Similarly, if a participant experienced multiple medical and surgical history events within the same SOC, the participant will be counted only once for that SOC. Medical and surgical history events will be sorted alphabetically by SOC and within each SOC the PT will be presented by decreasing order.

A listing of all medical and surgical history events will be provided.

## 10 PRIOR AND CONCOMITANT MEDICATIONS

Medications will be coded according to the World Health Organization Drug Dictionary (WHODD).

Prior medications are defined as any medication discontinued prior to the first study treatment dose. Concomitant medications are defined as any medication whose stop date is after the first study treatment dose. See [Appendix 1](#) for handling of missing dates for prior and concomitant medications.

Incidence of prior and concomitant medications will be tabulated by Anatomical Therapeutic Chemical Classification System (ATC) level 3, and PT using the safety set. A participant with the same medication taken multiple times will be counted only once for the corresponding PT. Similarly, if a participant has taken more than 1 medication within the same ATC level, the participant will be counted only once for that ATC.

In addition, prohibited medications will be reviewed and determined from the concomitant medications used prior to the database lock. A listing of all prior and concomitant medications will be provided, with a flag indicating prohibited medication used.

## 11 STUDY TREATMENT EXPOSURE AND TREATMENT COMPLIANCE

The study treatment will be applied twice daily (except on Day 28), at approximately the same times each day; the date and time of each application can be recorded in the eDiary, paper back up and in clinic. It is recommended that the application times be approximately 12 hours apart ( $\pm 2$  hours).

If an application is missed participants should apply the study treatment as soon as they remember on the same day. However, if it is the next day, the missed application should be skipped and the next application should be applied as normal. Participants are not to receive study treatment for more than 28 days.

In the case of application data are found in multiple sources, all available records will be used for analysis. An application recorded within 10 minutes on eDiary and paper back up is considered as one dose.

A summary of exposure will be summarized descriptively using the safety set by each treatment group including the number of days treated, total number of applications received and compliance during treatment, which is calculated as:

$$\frac{\text{The total number of IP Applications}}{(\text{The number of days between the last dose date and the first dose date} + 1) \times 2 - 1} \times 100$$

where the total number of IP applications include all valid doses even if they are over 28 days and the last dose date is calculated up to 28 days.

Descriptive statistics for compliance will be presented for each treatment group. Frequency distribution will also be presented for the following categories:

- $\leq 80\%$
- 80-100% (100% included)
- 100-120% (120% included)
- $> 120\%$

Study exposure and drug accountability data will be provided in a separate listing.

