3.2.2. Daily eDiary Entries

Participants will be required to complete eDiary entries to record information related to drug administration, emollient use, and peak pruritus NRS. Entries will be made in the web-based eDiary using the participant's own electronic device (smart phone, tablet, or any device with internet access and ability to receive text messages). On Day 1, site staff will assist with creating an eDiary account for the participant, ensuring that the participant can access the account using their own device, and providing instructions on making entries. At the Day 28 or End of Treatment Visit (after administration and documentation of the last dose of study drug), site staff will lock the participant's eDiary account and no further entries will be made.

On Day 1, eDiary entries will be made hourly from first dose to bedtime. After Day 1, eDiary entries will be made twice daily (at the time of dose administration) until Day 28. The following information will be recorded in the eDiary at the specified times:

- At the time of the morning dose administration, information on IP application and peak pruritus NRS will be recorded
- At the time of the evening dose administration, information on IP application and emollient use will be recorded

If for any reason a participant is unable to complete their eDiary (ie, the device battery dies, service is lost, etc.), they will record the information on a paper form. Any paper forms used for eDiary entries should be filed in the participant's source files.

Participants should recall and record missed eDiary information on the paper form as soon as they realize the entry was missed. In order to ensure the accuracy of the data, every effort should be made to record missed NRS data on the paper form within 24 hours of the missed entry. Sites are encouraged to work with the participant to complete a paper back-up diary for missed entries regarding IP application and emollient use at their in-clinic visits if not already completed by the participant. Recall of NRS should not exceed 24 hours.

At each study visit, participants should be reminded that they are required to make entries in the eDiary twice per day. Site staff will assess treatment compliance and eDiary completion compliance at each visit. Participants who are not compliant will be re-educated on the proper use of the study drug and the eDiary.

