5.3. Treatment Compliance

Treatment compliance will be monitored at each visit. Adherence to treatment will be assessed by direct questioning, review of the participant's dosing diary, and by maintaining adequate trial product dispensing and return records. Any deviation from the prescribed dosage regimen will be recorded in the source document and eCRF.

Participants who are significantly noncompliant with treatment (ie, administration of <80% of the expected treatments) based on IP accountability will be counseled and could be discontinued from the trial, at the discretion of the Investigator, following consultation with the Sponsor. A participant will also be considered significantly noncompliant if he or she intentionally or repeatedly takes more than the prescribed amount of trial product in the same time frame, as judged by the Investigator.

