If an application is missed participants should apply the study treatment as soon as they remember on the same day. However, if it is the next day, the missed application should be skipped and the next application should be applied as normal.

Participants will be trained on how to apply the study treatment on Day 1 with reminders given at each subsequent visit, which will be documented. Participants will apply their first dose (on Day 1) and their last dose (on Day 28) at the study site. When participants are dosed at the study site, they will self-apply the treatment under the direction and supervision of delegated study staff; the date and time of the application will be recorded by the site staff on the eCRF.

Participants are not to receive study treatment for more than 28 days.

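### The SAP's on-treatment compliance formula can overstate compliance, because its numerator, its fixed subtraction of 1 and its duplicate rule do not match the doses expected

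*SAP*

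**What the plan says.** SAP section 11 defines compliance during treatment as the total number of applications divided by a count of expected doses, times 100. The expected count is built from "The number of days between the last dose date and the first dose date", plus 1, times 2, minus 1. The applications counted "include all valid doses even if they are over 28 days and the last dose date is calculated up to 28 days". The same section also states: "Participants are not to receive study treatment for more than 28 days".

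Applications may be recorded in the eDiary, on the paper back-up and in clinic, and all available records are used. The only merging rule is: "An application recorded within 10 minutes on eDiary and paper back up is considered as one dose".

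Protocol section 6.1 asks for the date and time of every application in the eDiary. For the doses applied at the site on Day 1 and Day 28 it adds that "the date and time of the application will be recorded by the site staff on the eCRF". Protocol section 3.2.2 covers the paper form: "Participants should recall and record missed eDiary information on the paper form as soon as they realize the entry was missed".

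The SAP tabulates compliance descriptively in four bands: up to and including 80%, above 80 to 100%, above 100 to 120%, and above 120%. Separately, Protocol section 5.3 describes significant noncompliance as "administration of <80% of the expected treatments", judged on product accountability.

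**The concern.** A compliance percentage should compare doses taken with doses expected over the same period, counting each application once. The formula departs from this in three ways.

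- Applications after Day 28 are added above the line while the period below the line stops at Day 28, so late doses can cancel missed ones.
- The subtraction of 1 reflects the single dose on the last clinic day, but it is applied to everyone, including participants who stop early after a day with two doses.
- The merging rule leaves out clinic records, although the protocol has the two supervised doses written down in two places. It also leaves eDiary and paper entries more than 10 minutes apart as two doses, and paper times may be recalled.

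At stake is how well the exposure table describes what was applied. In a concentration-response trial, readers will look to that table when judging whether participants used the assigned gels. It can mask some under-dosing, and it can put adherent participants into the bands above 100%.

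**Working it through.** The documents give no compliance result to reproduce, so the check applies the formula to defined cases.

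**Inputs.** Two applications a day on Days 1 to 27 and one on Day 28 (SAP section 11; Protocol section 6.1). The formula, the Day 28 cap and the 10-minute rule come from SAP section 11. The dose counts in each case below are illustrations.

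**Formula.** Compliance = 100 × applications / (2 × D − 1), where D is the number of days from first dose to last dose, with the last dose taken no later than Day 28.

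**Base case.** Planned doses = 27 × 2 + 1 = 55. Formula denominator = 28 × 2 − 1 = 55. The formula is therefore right for a Day 28 completer with clean records.

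**1. Doses after Day 28**
- Full dosing to Day 29, with one dose on that day: 57/55 = 103.6%. To Day 30: 59/55 = 107.3%.
- 41 doses to Day 28 plus 4 later: 45/55 = 81.8%. Counting only doses to Day 28: 41/55 = 74.5%.
- 45 of the 59 doses possible to Day 30: 45/55 = 81.8%. Over matching days: 45/59 = 76.3%.

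**2. Early stop with two doses on the last day**
- All doses taken to Day 7: 14/(7 × 2 − 1) = 14/13 = 107.7%.
- All doses taken to Day 14: 28/27 = 103.7%. Over the days treated: 28/28 = 100%.
- 22 of 28 doses to Day 14: 22/27 = 81.5%. Over the days treated: 22/28 = 78.6%.
- Both doses on Day 1 and none after: 2/1 = 200%.

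**3. Duplicate records**
- All 55 doses taken, with the Day 1 and Day 28 site doses in both the eDiary and the eCRF: 57/55 = 103.6%.
- 44 true doses plus one duplicate: 44/55 = 80.0% becomes 45/55 = 81.8%.
- 43 true doses plus two duplicates: 43/55 = 78.2% becomes 45/55 = 81.8%.

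Each feature alone can move a participant from the lowest band to the next one.

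**Check on the remedy.** The protocol's schedule lets the Day 28 visit fall up to 2 days early, with the last dose applied at that visit. A fully adherent completer seen on Day 26 has 26 × 2 − 1 = 51 expected doses. The SAP formula gives 51/51 = 100%. A denominator fixed at 55 would give 51/55 = 92.7%, so a correction must not simply impose 55.

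**The case against.** Much can be said for the plan. The measure is labelled as compliance during treatment, so ending at the last dose fits its purpose and handles an early Week 4 visit correctly. The same summary gives days treated and total applications, so someone who stopped on Day 14 is visible as such. Treatment beyond 28 days is not allowed and the eDiary is locked at the Day 28 visit, so 14 missed doses combined with 4 late ones is a corner case. The SAP does merge some duplicates and refers to valid doses.

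These points limit the reach of the problem but do not remove it. The SAP itself provides for doses beyond 28 days. Its schedule also prints ±2 days for the Day 28 visit where the protocol prints −2; the two need reconciling. The minus 1 inflates the figure even over the days actually treated, so the label does not defend it. Section 11 does not say what makes a dose valid. Recording the site doses twice is a foreseeable result of following the protocol, which locks the eDiary only after the last dose has been documented.

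A reader might infer four stronger things that the documents do not support:

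- **That the plan prescribes double counting.** It does not. There is a merging rule, and the fault is a gap in it.
- **That anyone who stops early scores about 100%.** Doses missed between first and last dose still count against the participant: 14 of 28 doses to Day 14 gives 14/27 = 51.9%. Stopping after the morning dose on Day 14 with none missed gives 27/27 = 100%, not more.
- **That the formula cannot detect under-dosing.** A completer with 41 doses and clean records gets 74.5% and falls in the lowest band.
- **That crossing 80% triggers the protocol's noncompliance provision or removes someone from an analysis set.** The provision in Protocol section 5.3 rests on product accountability, and the per-protocol definition in SAP section 4.2 names no compliance percentage.

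**Conclusion.** The rule is wrong as written, with limited consequences. It can overstate compliance in three identifiable situations: doses after Day 28, an early stop after two doses on the last day, and applications recorded in more than one source that the 10-minute rule does not catch. In the illustrations the excess is about 2 to 7 percentage points, and more for very early stops (200% for two doses on Day 1 only). That is enough to cross the 80% or 100% band limit.

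The late-dose cases assume that such doses occur. The duplicate cases assume that site doses are entered in both sources and that the programmer does not remove the pair under an unstated validity rule. The documents do not show how many participants would be affected. Only the descriptive compliance figures and their bands change; no efficacy model or analysis set is defined by this formula.

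**What to change.** Amend SAP section 11 as follows.

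1. Count applications and expected doses over the same days: from the first dose to the Week 4 clinic dose, or to the last dose or treatment discontinuation if earlier, and not beyond Day 28.
2. Subtract 1 only when the final clinic dose was given. State how the last day is counted for an early stopper with one dose that day, because 27 doses to Day 14 is 27/27 = 100% with the subtraction and 27/28 = 96.4% without it.
3. Merge clinic, eDiary and paper records of the same application, with a stated source order, as SAP section 5.7.2 already does for the daily NRS. Cover eDiary and paper entries of one application that lie more than 10 minutes apart.
4. Report applications after Day 28 separately, as deviations.
5. Optionally add the share of the planned course, allowing for the protocol's −2 day visit window.

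The cost is a change of SAP wording and a small amount of programming, with no new data. The downside is that reported compliance may be slightly less favourable.
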